### **12.3. Statistical analyses**

Statistical analysis will be conducted according to the ITT principle, in which all randomized women will be conducted for the comparison of primary outcomes between treatment groups. The per-protocol analysis may be conducted, but these results would be considered reference only. All tests will be two-tailed, and differences with p-value < 0.05 will be considered statistically significant. The statistical software used was R, version 4.0.5 (R Foundation for Statistical Computing). We will develop a detailed statistical analysis plan that will be completed before data-lock.

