## 7.2. Screening and Enrollment

The patients will be checked for inclusion criteria on the second - fourth menstrual day (Visit 2). Laboratory tests (blood tests, urine test and ECG) will be taken for pre-anesthesia examination; in addition, the hormone values include FSH (follicle-stimulating hormone) – only for the first OS cycle, E2 (Estradiol), LH (Luteinizing hormone), P4 (Progesterone) and AMH if the result is not available within 6 months. A pre-anesthesia examination will be performed to ensure that the patient is eligible for the oocyte retrieval procedure.

On the day (Visit 2), screening for eligibility will be performed by treating physicians. If the patients are eligible, we will invite them to a full discussion about the Study and give the informed consent form. We will inform verbal and written consent and explain the relevant information such as study context, objectives, and data collection procedure. Patients will be given a period (3-4 hours) during anesthesia testing to understand the information and decide whether they agree to participate in the Study. The investigators will obtain written informed consent from all couples before enrolment. To maximize retention in the trial, a consultation will be available to couples to ensure they understand the procedures well and to address any questions or complaints that arise during the Study.

When there is an eligible participant to be enrolled in the Study, clinicians from the specific site will enter the study data management center to get the allocation of patients according to a computer-generated randomization list in a 1:1 ratio, with a variable block size of 2, 4, 6 or 8. After randomization, if a participant wishes to change her assigned protocol in the first cycle, she will be considered a crossover but analysed in the group she was assigned (intention-to-treat). However, if she wishes to change the assigned protocol from the second ovarian stimulation cycle or transfer more than one embryo after randomization, it will be considered a protocol violation and excluded from the analysis. Due to the type of interventions, this Study will be label-opened to clinicians who perform ovarian stimulation, oocyte retrieval, and embryo transfer.

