## **12. STATISTICAL CONSIDERATIONS**

### **12.1. Sample size determination**

The ongoing pregnancy rate of patients in ART center – Tam Anh HCM hospital was 45.0% in the Antagonist IVF stimulation group. To show or refute that hypothesis: no significant difference in ongoing pregnancy rates when using DPOS protocol (40 - 42%) (43–45), we need 657 patients to produce a two-sided 95% confidence interval for the difference in population proportions with a width that is equal to 5% (margin = 5.0%, alpha = 5.0% and power = 80%). Considering a 10% loss to follow-up and protocol violation we plan to recruit 730 participants (365 per arm).

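### The per-protocol analysis is optional and without weight, although the trial may conclude 'no difference' and first-cycle crossovers stay in their assigned arm

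*Protocol*

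**What the plan says.** Section 12.3 makes ITT, on every woman randomized, the comparison for the primary outcome. On the alternative set it says: "The per-protocol analysis may be conducted, but these results would be considered reference only".

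Section 12.1 frames the question as one of similarity: "To show or refute that hypothesis: no significant difference in ongoing pregnancy rates when using DPOS protocol". It gives the planning values as "margin = 5.0%, alpha = 5.0% and power = 80", a control rate that "was 45.0% in the Antagonist IVF stimulation group", and a DPOS rate of 40 to 42%.

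Section 7.2 deals with changes of regimen. Of a woman who changes in the first cycle it says: "she will be considered a crossover but analysed in the group she was assigned (intention-to-treat". A change from the second cycle on, or transfer of more than one embryo, is instead called a protocol violation, and those women are left out of the analysis.

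Section 12.3.2 tests the primary outcome with a chi-square or Fisher test and reports a risk ratio; the margin is not used. Section 12.3.4 offers sensitivity analyses for loss to follow-up and protocol violation, without fixing their content.

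**The concern.** ITT alone is the cautious choice when the aim is to show a difference, because crossover works against the claim. When the conclusion at stake is that two regimens do not differ, crossover works for it: a woman counted in the DPOS arm but treated with the antagonist, or the reverse, makes the arms more alike. The usual check is to see whether women treated as assigned tell the same story. Here that check may be skipped, and it carries no weight if it is done.

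Nothing else in the protocol fills the gap. Section 7.2 separates crossovers from protocol violations, so the sensitivity analyses in section 12.3.4, as worded, do not reach first-cycle crossovers. Crossover is also plausible: the trial is open-label, one regimen is a tablet and the other a daily injection, and section 2.1 calls the oral regimen cheaper and easier for patients.

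At stake is the credibility of a no-difference statement. In an open-label trial an optional analysis can also be run, dropped or played down once the results are known.

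**Working it through.** **The plan's own figures.** 657/(1 − 0.10) = 730 reproduces. The 657 itself does not follow from the stated inputs: a 95% interval with half-width 5 points needs 1500 to 1510 women at DPOS rates of 40 to 42%, and a two-sided test with 80% power needs 3068 (45% v 40%) to 8572 (45% v 42%). This is a separate matter, but it sets the background for what follows.

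**Inputs.** n = 365 per arm, control 45%, DPOS 40 to 42% and two-sided 5% tests, all from section 12. A DPOS rate of 35% is added as an assumption, to show a larger deficit. The crossover fraction c is not in the protocol; c = 10% is assumed, and smaller and larger values are shown below. Switchers are assumed to take on the rate of the regimen they receive.

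**Dilution.** For a true difference d, the ITT difference is d(1 − c) if one arm switches and d(1 − 2c) if both do. At c = 10%, 5 points become 4.5 or 4.0, and 10 points become 9 or 8.

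**Chance of a non-significant result.** This is 1 − Φ[(d − 1.96·SE0)/SE1], with SE0 the pooled and SE1 the unpooled standard error. One-arm switching is taken in the DPOS arm. All entries in the middle columns are in percentage points.

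| True rates | Crossover | ITT difference | 1.96·SE0 | SE1 | Non-significant |
|---|---|---|---|---|---|
| 45 v 40 | none | 5.0 | 7.17 | 3.65 | 72.4% |
| 45 v 40 | 10%, one arm | 4.5 | 7.18 | 3.66 | 76.8% |
| 45 v 40 | 10%, both arms | 4.0 | 7.17 | 3.66 | 80.7% |
| 45 v 42 | none | 3.0 | 7.19 | 3.67 | 87.3% |
| 45 v 42 | 10%, both arms | 2.4 | 7.19 | 3.67 | 90.4% |
| 45 v 35 | none | 10.0 | 7.11 | 3.61 | 21.1% |
| 45 v 35 | 10%, one arm | 9.0 | 7.12 | 3.62 | 30.2% |
| 45 v 35 | 10%, both arms | 8.0 | 7.11 | 3.61 | 40.2% |

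Example for the first row: (5.0 − 7.17)/3.65 = −0.59, so power is 27.6% and the chance of a non-significant result is 72.4%.

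**Other crossover rates, both arms.** At 45% v 40% the chance is 74.2% at c = 2%, 76.8% at 5% and 87.3% at 20%. At 45% v 35% it is 24.5%, 30.0% and 62.0%.

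**What a per-protocol set would add.** Suppose 10% of each arm is dropped as switchers, leaving about 328 per arm (365 × 0.9), with no selection bias. The full difference returns, and the chance of a non-significant result is 74.7% at 5 points and 25.5% at 10 points. ITT with 10% crossover in both arms gives 80.7% and 40.2%. Two analyses cannot both be non-significant more often than either one alone, so requiring agreement limits a false no-difference reading to at most 74.7% and 25.5%.

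**Why the set must keep women without a blastocyst.** Section 8 counts them as failures. Assume 54.2% success per transfer in both arms, with a transfer reached by 83% of controls (the introduction cites 17.0% of cycles without a usable blastocyst) and by 73.8% of DPOS women. Per patient this is 0.542 × 0.83 = 45.0% v 0.542 × 0.738 = 40.0%. Among women with a transfer the difference is zero. A set defined by having had a transfer would hide that deficit.

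**The case against.** **The trial can be read as a test of difference.** The objective is to compare, the test is two-tailed, and ITT with a supportive per-protocol analysis is then conventional. This stands as far as keeping ITT primary. It does not remove the point, because section 12.1 names no significant difference as the hypothesis and a null result would be read as support for it.

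**A reader might infer an inflated non-inferiority error.** If the lower 95% limit were read against −5 points with a true 5-point deficit, the error would rise from 2.5% to 3.4% at 4.5 points and 4.6% at 4.0 points. The protocol states no such rule, so these figures are conditional on a decision the plan does not contain.

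**A reader might infer that the trial expects crossover on a material scale.** Section 7.2 only provides for it, in the conditional, and gives no rate. With few switchers the effect is small.

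**Low power matters more.** At 45% v 40% nearly three results in four are non-significant with no crossover at all, and agreement with a clean per-protocol set would still let up to about 75% through. This stands. The remedy here does not make non-significance evidence of similarity.

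**Part of the dilution may already be removed.** Section 7.2 leaves later-cycle switchers out of the analysis. That too stands as written, so the calculation concerns first-cycle crossovers only. It also shows that sections 7.2 and 12.3 conflict on who is analysed.

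**The analysis plan is still to come.** The protocol has already fixed the per-protocol analysis as optional and for reference only, and a plan consistent with it would inherit that.

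**Conclusion.** The point holds in a limited form. The protocol allows a no-difference conclusion to rest on ITT alone, keeps first-cycle crossovers in their assigned arm, and gives no weight to the analysis that would show whether crossover produced the result. The direction of the bias is clear if switchers take on the rate of the regimen they receive. The size depends on an assumed crossover rate: at 10%, the chance of a non-significant result rises by about 4 to 8 percentage points at 45% v 40% (72% to 77% or 81%), and by about 9 to 19 points at 45% v 35% (21% to 30% or 40%).

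The documents do not support a claim that crossover will be frequent, that a non-inferiority error rate is breached, or that ITT should give way to per-protocol. This is a worthwhile and inexpensive correction, secondary to the sample size.

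**What to change.** Keep ITT on every woman randomized as the primary analysis. Replace the per-protocol sentence in section 12.3 with:

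> A per-protocol analysis will be performed and reported beside the ITT analysis. The set is fixed before data-lock and comprises women who received their assigned protocol in every stimulation cycle undertaken and had no transfer of more than one embryo; women with no blastocyst for transfer are retained and counted as failures. A conclusion that the regimens do not differ will be drawn only if the ITT and per-protocol 95% confidence intervals for the difference support the same conclusion; any discordance will be reported.

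Reconcile section 7.2 with section 12.3, so that leaving out later-cycle switchers and women with more than one embryo transferred applies only to the per-protocol set.

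Cost: a few sentences and one further run of the same analysis. The per-protocol set is not randomised and is open to selection bias, so it can only support ITT, and a no-difference claim becomes somewhat harder to make. The change does not repair the low power.

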#### *12.3.1. Characteristics of patients*

Patient's characteristics will be shown through descriptive analysis, and the balance between the two arms will be assessed. For continuous variables, the normality test will be estimated using frequency histograms and the

Shapiro's test. If the parameters are normally distributed, they will be presented as mean with standard deviation (SD) and compared using Student's t-tests or ANOVA tests. If the parameters are non-normally distributed, their medians and inter-quantile ranges (IRQs) will be reported, and non-parametric tests will be utilized to test the distribution of these variables. For categorical variables, data will be shown by the proportions of the two arms, and they will be compared using Pearson's chi-square test or Fisher's exact test where appropriate. In addition, we will also report the numbers of recruitment, participants lost to follow-up, protocols violation, and other relevant descriptive data.

#### *12.3.2. Primary outcome*

The primary outcome, ongoing pregnancy rate will be compared using Pearson's chi-square test or Fisher's exact test for unadjusted analysis. We will also compute the unadjusted risk ratio (RR) and its 95% confidence interval (95% CI). In the event of a prominent imbalance of potential confounders between arms, we will perform multivariable Log-Binomial or Poisson Regression with a robust variance estimate to compute adjusted RR and its 95% CI.

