## **1. STATEMENT OF COMPLIANCE**

The trial will be conducted in accordance with the International Conference on Harmonisation Good Clinical Practice (ICH GCP), applicable Vietnamese Code of Federal Regulations (CFR), Terms and Conditions of Award. The Principal Investigator will assure that no deviation from, or changes to the protocol will take place without prior agreement from the Investigational New Drug (IND) or Investigational Device Exemption (IDE) sponsor, funding agency, and documented approval from the Institutional Review Board (IRB), except where necessary to eliminate an immediate hazard(s) to the trial participants. All personnel involved in the conduct of this Study have completed Human Subjects Protection and ICH GCP Training.

The protocol, informed consent form(s), recruitment materials, and all participant materials will be submitted to the IRB for review and approval. Approval of both the protocol and the consent form must be obtained before any participant is enrolled. Any amendment to the protocol will require review and approval by the IRB before the changes are implemented in the Study. All changes to the consent form will be IRB approved; a determination will be made regarding whether a new consent needs to be obtained from participants who provided consent, using a previously approved consent form.

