#### *12.3.6. Planned interim analyses*

The interim analysis will be performed by an independent statistician who will not be directly involved in the Study, after the completion of data collection of the first 366 randomized patients. In interim analyses, data will be assessed for safety, efficacy, and futility. Safety will be assessed in terms of serious adverse events. The interim analysis will be conducted using a two-sided significant test with the Haybittle–Peto spending function and a type I error rate of 5% with stopping criteria of  $p < 0.001$ . According this report, the DSMB will guide whether to stop or continue the Study.

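### The adjusted risk ratio for ongoing pregnancy is run only if a prominent baseline imbalance appears; always running it with pre-named covariates is a slightly more efficient rule

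*Protocol*

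**What the plan says.** Protocol section 12.3.2 gives the analysis of the primary outcome. The part that is always run is unadjusted: "ongoing pregnancy rate will be compared using Pearson's chi-square test or Fisher's exact test for unadjusted analysis", together with an unadjusted RR and its 95% confidence interval. The adjusted RR, by log-binomial or robust Poisson regression, is conditional: "In the event of a prominent imbalance of potential confounders between arms, we will perform multivariable Log-Binomial or Poisson Regression". The section names no covariates and no threshold, and does not say which RR leads if both are produced.

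Section 12.3.1 describes the baseline comparison, in which "the balance between the two arms will be assessed" using between-arm significance tests. Section 12.3 sets the general level: "All tests will be two-tailed, and differences with p-value < 0.05 will be considered statistically significant". It also promises a detailed analysis plan before data-lock. Section 12.2 describes 1:1 allocation in blocks of varying size and states no stratification factor. No section plans an adjusted analysis in all cases.

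**The concern.** In a randomised comparison, baseline imbalance arises by chance. The average value of adjusting for a covariate depends on how well it predicts the outcome, which can be judged in advance. A rule that waits for an imbalance settles the question on a chance event, after the baseline data are seen, and forgoes the gain in every trial where the condition is not met.

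The analysis plan could define *prominent* or list covariates, and their absence here is not the complaint. The protocol itself has fixed the conditional rule. At stake is a small loss of precision in the main comparison, plus some avoidable discretion in an open-label trial.

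**Working it through.** **Inputs from the protocol.** Control rate 45%, DPOS rate 40-42%, 657 evaluable women and 10% loss (section 12.1). The recruitment target reproduces: 657/(1 − 0.10) = 730, or 365 per arm. This point does not depend on how 657 was reached.

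**Assumptions, not in the protocol.** Three covariates: age, AMH and site. 30% of women are at the second site. *Prominent* is read as p<0.05 on any of the three. Covariate strength is shown as a range, as log odds ratios (age per SD / AMH per SD / site): none 0/0/0; weak 0.2/0.1/0.2; mid 0.3/0.2/0.3; moderate 0.5/0.3/0.4; strong 0.6/0.5/0.5.

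**Step 1: how often the condition is met.** For k independent covariates the chance is 1 − 0.95^k:
- k = 3: 0.143
- k = 5: 0.226
- k = 10: 0.401

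In simulation (N = 730, 4,000 runs per setting) the rate was 13-15% in every setting, from no prognostic value to strong.

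**Step 2: average precision gain from always adjusting.** The table gives the simulated mean variance ratio of the log RR (robust Poisson, adjusted over unadjusted), and the equivalent sample size as 730/ratio.

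| Strength | Variance ratio | Variance reduction | Equivalent N | Extra women |
|---|---|---|---|---|
| none | 1.000 | 0% | 730 | 0 |
| weak | 0.9865 | 1.4% | 740 | 10 |
| mid | 0.967 | 3.3% | 755 | 25 |
| moderate | 0.927 | 7.3% | 788 | 58 |
| strong | 0.886 | 11.4% | 824 | 94 |

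**Step 3: what that means for the interval.** At 45% in both arms, SE(log RR) = √(2 × 0.55/(0.45 × 365)) = 0.0818. The 95% interval around RR 1.00 is exp(±1.96 × SE × √ratio):
- unadjusted: 0.852-1.174
- weak: 0.853-1.173
- strong: 0.860-1.163

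**Step 4: power.** Two-sided 5%, normal approximation, with n the effective number per arm: Φ{[Δ − 1.96√(2p̄(1−p̄)/n)] / √[(p₁(1−p₁)+p₂(1−p₂))/n]}.
- 45% vs 40%, n = 365: (0.05 − 0.0717)/0.0365 = −0.594, so 27.6%. Adjusted: 27.9% (weak) to 30.5% (strong).
- 45% vs 42%: 12.7% unadjusted; 12.8% to 13.7% adjusted.

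Simulation at 45% vs 40% gave 27.5% to 27.6% (weak) and 27.1% to 30.8% (strong), with Monte Carlo error of the paired difference up to about 0.5 points. A separate simulation at N = 656, with strong covariates explaining about 9% of outcome variance, gave 26.1% unadjusted, 26.2% under the imbalance-triggered rule and 28.2% always adjusted. The triggered rule recovers little of the gain.

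**Step 5: where the gain lies.** The mean squared error (MSE) of the log RR counts the error that chance imbalance puts into the estimate. Ratios adjusted/unadjusted, at 45% in both arms and N = 730, from two simulations:

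| Strength | Met / not met (6,000 runs) | Met / not met (4,000 runs) |
|---|---|---|
| weak | 0.985 / 0.990 | – |
| mid | 0.917 / 0.978 | 0.90 / 0.98 |
| moderate | 0.833 / 0.950 | 0.85 / 0.95 |
| strong | 0.768 / 0.915 | 0.74 / 0.93 |

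Except with weak covariates, adjustment helps most where the condition is met. Those trials are the minority, however. With strong covariates the absolute MSE reduction is 0.00191 when met and 0.00057 when not. Weighted by frequency this is 0.143 × 0.00191 = 0.00027 against 0.857 × 0.00057 = 0.00049, so about 64% of the total gain lies where the condition is not met. With moderate covariates the figures are 0.143 × 0.00128 = 0.00018 against 0.857 × 0.00033 = 0.00028, about 61%.

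**Step 6: type I error.** At N = 730, null rejection was 4.6-4.9% unadjusted and 4.5-5.3% always adjusted. At N = 656 it was 4.3-5.6% across the unadjusted, triggered and always-adjusted rules.

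**Step 7: two results without a stated lead.** If both are always reported at 45% vs 40%, their p-values fall on opposite sides of 0.05 in 3% (weak) to 11% (strong) of trials.

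**The case against.** The strongest reply is that nothing invalid is planned. The unadjusted test and RR are always produced, the adjusted RR only adds to them, and an unadjusted primary analysis with a supplementary adjusted one is an accepted choice. That stands, and it limits this to an efficiency point.

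A reader might infer that the trigger is unrelated to the benefit of adjusting. The model-based variance ratio seems to support this: with strong covariates it is 0.892 when the condition is met and 0.886 when it is not. But that ratio worsens whenever treatment correlates with covariates, and it cannot show the error that adjustment removes. The MSE in step 5 can, and it shows the trigger partly selecting the trials where adjusting helps most. What survives is that the firing rate ignores prognostic strength, and that an always-run model covers those trials too.

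It is also fair that the size is assumed. The protocol gives no prognostic strengths, site split or threshold. Age is limited to 18-37 and ovarian reserve is restricted (section 6.1), and oocytes are accumulated towards a common target (section 5). All of this could make age and AMH weak predictors. The 86% of trials in which the condition is not met (1 − 0.143) holds only for three covariates at p<0.05; with five it is 77% and with ten 60%.

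Finally, changing the primary estimate mid-trial carries its own risks: the interim test, missing covariates and timing. Those objections are sound, and the fix has to answer them.

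**Conclusion.** The point holds as a minor improvement. The protocol makes adjustment depend on a chance event whose frequency is unrelated to covariate strength, and so gives up a small gain in most trials. Over assumed strengths from none to strong, always adjusting lowers the variance of the log RR by about 0-11% and adds about 0-3 points of power at 45% vs 40%. With weak covariates the benefit is close to nil.

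A reader might go further and conclude that the conditional rule biases the primary result or inflates its false-positive rate. The protocol does not support that: the unadjusted result is always reported, and simulated null rejection stayed near 5%.

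The conclusion rests on the assumed covariate strengths, the 30% share at the second site, and the p<0.05 reading of *prominent*. The direction does not depend on their exact values; the size does.

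**What to change.** Replace the conditional sentence in section 12.3.2 with wording such as:

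> In all cases an adjusted RR will be estimated by Poisson regression with robust variance, adjusted for age, AMH (continuous) and site, in all randomised women, with missing baseline covariates imputed so that no woman is dropped. The adjusted RR is the primary estimate; the unadjusted test and RR are supportive.

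The imputation clause is needed because section 12.3.4 first analyses the data with missing baseline values excluded, which could remove women from the intention-to-treat estimate. Section 12.3.6 should also state which of the two results feeds the p<0.001 interim rule.

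Settle this before any outcome data by arm are reviewed, including the interim analysis due "after the completion of data collection of the first 366 randomized patients". The summary of changes reports 272 women recruited by August 2024, so timing matters. If such data have already been reviewed, keep the unadjusted test and RR as primary and always report the adjusted RR as supportive. The precision gain then reaches only the supportive estimate.

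The cost is a protocol amendment or an entry in the analysis plan. For an amendment, section 1 applies: "Any amendment to the protocol will require review and approval by the IRB before the changes are implemented in the Study". Section 12.3.5 also has the DSMB review protocol revisions. No new data are needed: age and AMH are eligibility variables (section 6.1), AMH is measured before enrolment (sections 7.1 and 7.2), and site is known. The remaining downside is a model-based headline result in place of a simple chi-square comparison.
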